6.6 Restrictions

6.6.1 Prior Therapy

Prior therapy restrictions are described in the inclusion/exclusion criteria specified in Section 3.

6.6.2 Fluid and Food Intake

There are no requirements for fasting and no restrictions for fluid and food intake by the patients during the study.

6.6.3 Patient Activity Restrictions

There are no restrictions on patient activities and no requirement for patient confinement during the study.

6.7 Treatment Compliance

MGA271 will be administered by healthcare professionals under the supervision of the Investigators. Records of MGA271 dose calculation, administration, and dosing regimen will be accurately maintained by site staff. The monitor will review dose calculation, administration and regimen as well as medication accountability during investigational site visits and at the completion of the study.

6.8 Packaging and Labeling

MGA271 will be supplied in bulk, open-label, single-use vials. All investigational product will be labelled with a minimum of the protocol number, directions for use, storage conditions, expiry date (if applicable), batch number, the statements "For clinical trial use only," and/or "CAUTION: New Drug – Limited by Federal (United States) Law to Investigational Use," and the Sponsor's name and address. Please see the Pharmacy Manual for detailed information about the packaging of the study drug.

6.9 Storage and Accountability

The vials containing study drug should be stored at 2° – 8° C (36° – 46° F) and must not be frozen or shaken. Protect from sunlight. To ensure compliance with storage conditions, temperature logs will be maintained.

Because there is no preservative and drug loss occurs over time, administration of study drug should begin immediately after preparation but no later than 6 hours after preparation (see Pharmacy Manual). If there is a delay in administration of study drug such that it will not be administered on the day of preparation, the Clinical Project Manager should be notified immediately. Instructions on how to proceed will be provided. The Investigator or his/her designee is required to maintain accurate drug accountability records. A binder containing instructions and the required accountability documentation will be provided to the Investigator or his designee. When the study is completed, copies of study drug accountability records must be sent to the Sponsor. The original drug accountability records must be maintained with the rest of the documentation in accordance with Section 9.3 of the protocol.

Additional details regarding storage, handling, and accountability can be found in the Pharmacy Manual.

6.10 Investigational Product Disposition at End of Study

Upon completion or termination of the study, all unopened vials of study medication must be returned to MacroGenics or its representative, unless the site has received written authorization from MacroGenics to destroy study drug at the site. All drug returns to MacroGenics or its representative must be accompanied by the appropriate documentation and be clearly identified by protocol number and study site number on the outermost shipping container. If MacroGenics approves the destruction of drug at the site, the Investigator must ensure arrangements are made for proper disposal and that appropriate records of disposal are documented and maintained and copies provided to the Sponsor.

7. ADVERSE EVENTS AND REPORTING REQUIREMENTS

An adverse event (AE) is defined as any untoward medical occurrence (symptom, sign, illness or experience) that develops or worsens in a research patient during a clinical study or within 30 days post-treatment, regardless of causality. This includes adverse clinical or laboratory findings, any adverse drug reaction (ADR), an illness with onset during the study, or an exacerbation of a preexisting illness or condition. Cancer progression should not be considered an AE, unless the investigator believes that the study treatment exacerbated the patient's condition. Exceptions are if disease progression results in death or hospitalization while a patient is on study, in which case the disease progression is considered a serious AE. Abnormal findings on physical examination or diagnostic procedures are also considered AEs if: they are associated with clinical signs or symptoms; they require therapeutic intervention or additional diagnostic testing; they lead to dose modifications/termination of the study drug; or they are considered clinically significant by the investigator. All observed or reported AEs, regardless of their suspected causal relationship to the study drug, should be recorded on the Case Report Form (CRF).

The NCI CTCAE version 4.0 will be used for adverse event descriptions and grading (http://ctep.cancer.gov/protocolDevelopment/electronic applications/docs/ctcaev3.pdf). These criteria are summarized in Appendix B. The type and severity of an AE, as well as its potential link to the study drug(s), will determine whether the event requires expedited reporting in addition to routine reporting. For all AEs, the investigator must pursue and obtain information to adequately determine the causality and outcome of the event, and to assess whether it meets criteria for a serious AE. In addition, follow-up of AEs should continue until the event and any sequelae resolve or stabilize at a level acceptable to the investigator and/or the medical monitor.

7.1 Recording and Grading

7.1.1 Recording

All observed or volunteered adverse events, regardless of treatment group, severity, suspected causality, expectedness, or seriousness will be documented on the CRF.

A clinically significant change in a physical examination finding or an abnormal test result (*i.e.*, laboratory value) should be recorded as an AE, if it:

- is associated with accompanying symptoms
- requires additional diagnostic testing or medical or surgical intervention
- leads to a change in study dosing or discontinuation from the study
- requires additional concomitant drug treatment or other therapy, or
- is considered clinically significant by the investigator

An abnormal test result that is subsequently determined to be an error does not require recording as an AE even if it originally met one or more of the above criteria.

7.1.2 Grading severity

All adverse events will be graded for intensity on a scale of 0 to 5, according to the NCI CTCAE version 4.0 (see Table 2 and Appendix B). These criteria can be found at http://ctep.cancer.gov/protocolDevelopment/electronic applications/docs/ctcaev3.pdf

Table 2 Intensity of Adverse Event

Grade	Description
0 (none)	No adverse event or within normal limits.
1 (mild)	Transient or mild discomfort; generally non-progressive; no limitation in daily activities; no medical intervention required.
2 (moderate)	Mild/moderate limitation in daily activities; some assistance may be required; no/minimal medical intervention required.
3 (severe)	Marked limitation in daily activities; some assistance usually required; medical intervention is required.
4 (life- threatening)	Extreme limitation in daily activities; major assistance required; significant medical intervention required.
5 (death)	Fatal adverse event.

7.1.3 Attributing causality

After grading for severity, the investigator must evaluate all clinical AEs and abnormal laboratory values for possible causal relationship to the study drug(s). Causality attribution will be decided using the criteria outlined in Table 3.

Table 3 Relation	ship of Adverse Event to Study Drug
Relationship	Description
Unrelated	AE is clearly not related to the study drug (An event that does not meet any of the criteria below).
Unlikely	AE is doubtfully related to the study drug (An event that follows a reasonable temporal sequence after drug administration; that follows a known or expected response pattern; but that could more reasonably be

explained by other characteristics of the patient's clinical state).PossibleAE may be related to the study drug (An event that follows a reasonable
temporal sequence after drug administration; that follows a known or

Protocol Version 2.0 (Amendment 2) / Version Date: 04/17/2019

IRB#: IRB0010377

	expected response pattern; but that could just as readily be attributed to a number of other factors).
Probable	AE is likely related to the study drug (An event that follows a reasonable temporal sequence after drug administration; that follows a known or expected response pattern; that is confirmed by stopping/reducing the drug dose; and that could not be reasonably explained by the characteristics of the patient's clinical state).
Definite	AE is clearly related to the study drug (An event that follows a reasonable temporal sequence after drug administration; that follows a known or expected response pattern; and that is confirmed by improvement on stopping/reducing the drug dose and reappearance on repeated exposure).

Abnormal laboratory values of clinical significance that were present at baseline and did not change in severity or frequency during experimental therapy and those that can obviously be attributed to underlying disease will be recorded as unrelated and will not be considered when evaluating study drug toxicity.

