2.3.2 Rationale for dosage selection

In the CP-MGA271-01 Phase I study, dose escalation was carried out from 0.01 mg/kg to 15 mg/kg without a DLT observed at any dose level. As 15 mg/kg was the highest protocol specified dose, 15 mg/kg was determined as the maximum administered dose (MAD), and that dose carried into the expansion phase of that study. The safety profile of MGA271 based on a total of 51 patients exposed to MGA271 demonstrated that the majority of AEs were mild (CTCAE Grade 1 or 2), with toxicities manageable by standard medical therapy. One patient has discontinued MGA271 for a drug related toxicity that was considered to be a drug-related SAE. (See **Investigator's Brochure version 8** for a more detailed description of the safety profile from Study CP-MGA271-01).

Preliminary PK modeling indicates that MGA271 administered at doses below 5 mg/kg IV on a weekly schedule follows a target-mediated drug disposition model. At doses above 5 mg/kg, exposure increased approximately linearly with the dose (See **Investigator's Brochure version 5, Table 9).** At doses above 5 mg/kg, linear two-compartment model with clearance, CL=0.201 L/day; central volume, V_c=3.22 L; inter-compartment clearance, Q=0.700 L/day; and peripheral volume, V_p= 3.68 L, provided adequate description of the observed data. The distribution half-life (i.e., the initial rapid distribution to tissues $[T_{1/2\alpha}]$) and the terminal half-life $[T_{1/2\beta}]$ were estimated at 1.6 days and 25 days, respectively.

IRB#: IRB0010377

Johns Hopkins University

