6.4.5.1 Grade 1 or 2 AEs

Study drug administration may continue despite observation of drug-related low grade adverse events (CTCAE grade 1 or 2). If the investigator in his/her medical judgment considers that a low grade AE is of clinical significance or inordinately prolonged, the Investigator may, at his/her discretion, delay treatment to allow for resolution. Necessity to delay for more than two consecutive doses will require the patient to permanently discontinue study drug. Study drug should also be discontinued for prolonged Grade 2 AEs lasting \geq 14 days that are at least possibly related to study drug. No dose reductions are allowed.

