6.4.5.2 Grade 3 or 4 AEs

Drug administration should be held upon observation of AEs of \geq Grade 3 severity to enable patient management, monitoring of the resolution of the event, and assessment of the relatedness of the event. An AE of \geq Grade 3 that is considered related to MGA271 will result in discontinuation of therapy unless otherwise specified in the protocol. For AEs associated with liver function test abnormalities, drug administration should also be discontinued for concomitant ALT >3xULN and total bilirubin >2x ULN without an alternative etiology (Hy's Law).

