Important medical events that may not result in death, be life-threatening, or require hospitalization may be considered serious when, based upon appropriate medical judgment, they may jeopardize

IRB#: IRB0010377

the patient or research subject and may require medical or surgical intervention to prevent one of the outcomes listed as serious.

Mandatory Safety Reporting

• **Initial reporting:** IND application sponsor must report any suspected adverse reaction or adverse reaction to study treatment that is both serious and unexpected.

Unexpected serious suspected adverse reactions suggesting significant risk to human subjects must be reported to FDA as soon as possible but no later than within **15 calendar days** following the sponsor's initial receipt of the information.

Unexpected fatal or life-threatening suspected adverse reactions represent especially important safety information and must be reported to FDA as soon as possible but no later than **7 calendar days** following the sponsor's initial receipt of the information.

• **Follow-up reporting:** Any relevant additional information obtained by the sponsor that pertains to a previously submitted IND safety report must be submitted as a Follow-up IND Safety Report. Such report should be submitted without delay, as soon as the information is available but no later than 15 calendar days after the sponsor receives the information.

All IND safety reports must be submitted on Form 3500A and be accompanied by Form 1571. The type of report (initial or follow-up) should be checked in the respective boxes on Forms 3500A and 1571.

The submission must be identified as:

- *"IND safety report" for 15-day reports, or*
- "7-day IND safety report" for unexpected fatal or life-threatening suspected adverse reaction reports, or
- "Follow-up IND safety report" for follow-up information.

The report must be submitted to an appropriate Review division that has the responsibility to review the IND application under which the safety report is submitted. Each submission to this IND must be provided in triplicate (original plus two copies). Send all submissions to the following address:

Food and Drug Administration Center for Drug Evaluation and Research Division of Oncology Products 1 [name] [name] 20705-1266

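### Table 3 has no related category for a well-timed adverse event whose pattern is neither known nor expected, which conflicts with the reporting standard in Section 7.5.1

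*Combined protocol and SAP*

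**What the plan says.** Section 7.1.3 makes the table binding: "Causality attribution will be decided using the criteria outlined in Table 3". The levels are Unrelated, Unlikely, Possible, Probable and Definite. Unrelated is described as clearly not related to the drug and, in brackets, "An event that does not meet any of the criteria below". Each of the other four opens with the same joint condition, "An event that follows a reasonable temporal sequence after drug administration; that follows a known or expected response pattern", and then adds its own terms.

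Section 7.5.1 uses another test. A suspected adverse reaction needs only a reasonable possibility of causation, explained as evidence suggesting a causal link, with no condition on pattern. It then states that the "IND application sponsor must report any suspected adverse reaction or adverse reaction to study treatment that is both serious and unexpected". Section 7.2 describes an unexpected event as one not associated with the agent in nature or intensity.

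Attribution is used in several places. Under 6.4.5.2 an event of grade 3 or higher "that is considered related to MGA271 will result in discontinuation of therapy unless otherwise specified in the protocol". Section 6.4.5.1 ties discontinuation for prolonged grade 2 events to their being at least possibly related. Section 7.3 has SAEs more than 30 days after the last dose recorded only if causation is suspected. Section 7.5.2 sets 3 or 15 days for IRB/IBC reports partly by relatedness. Section 7.4 sends perioperative events through Section 7.1. Section 10.4.1 summarises adverse events by causality, among other features.

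**The concern.** A causality scale should let an investigator suspect the drug when a new kind of event follows dosing closely. This one asks first whether the event resembles something already known or expected. If not, all four higher levels are closed, however good the timing and however weak the other explanations. Those are the events for which a serious-and-unexpected reporting duty exists.

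Safety, tolerability and feasibility are primary objectives, and there is no control arm against which an excess of some event could be seen. Causality judgement therefore carries more weight here than in a randomised comparison. If the table is followed literally, the drug-related column of the safety tables would omit new toxicities, and the provisions that depend on relatedness would not be triggered for them.

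**Working it through.** The plan gives no figure to reproduce, so the check is a reading of Table 3 row by row, followed by a trace of where the result is used.

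**Step 1. What each row requires.**

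| Row | Plausible timing | Known or expected pattern | Further condition |
|---|---|---|---|
| Unlikely | required | required | better explained by the patient's clinical state |
| Possible | required | required | other factors explain it equally well |
| Probable | required | required | confirmed on stopping or reducing; not reasonably explained by clinical state |
| Definite | required | required | improves on stopping or reducing, and returns on re-exposure |
| Unrelated | – | – | clearly not related; meets none of the criteria below it |

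The pattern condition stands in 4 of the 4 rows above Unrelated. Even the weakest of them reads "that follows a known or expected response pattern; but that could more reasonably be" explained otherwise, so the condition is joined to the rest and is not an alternative to it.

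**Step 2. A test event.** Take an event with plausible timing whose pattern is neither known nor expected. It fails the pattern condition and so satisfies 0 of the 4 rows.
- If the criteria in the Unrelated row are whole rows, the event meets none and is Unrelated.
- If they are single conditions, it meets one (timing), so it is not Unrelated either, and no category is left.

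No sentence in 7.1.3 or elsewhere overrides the table or assigns this case.

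**Step 3. The same event under 7.5.1.** If there is evidence suggesting a causal link, it is a suspected adverse reaction whatever its pattern. If it is also serious and unexpected, the sponsor must report it. Table 3 and 7.5.1 can thus give opposite answers for one event.

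**Step 4. Where the answer matters.**

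| Use | Depends on causality? |
|---|---|
| Recording on the CRF (7.1.1) and frequencies by grade (8.2.1, 10.2.1) | No |
| SAE notice to the IND sponsor within 24 hours (7.5.2) | No |
| Toxicity stopping rule (10.2.1) | Only for local reactions, a named event type |
| Summary by causality (10.4.1) | Yes |
| Discontinuation (6.4.5.1, 6.4.5.2) | Yes |
| SAEs more than 30 days after the last dose (7.3) | Yes, unless the patient still counts as on study |
| IRB/IBC timing, 3 or 15 days (7.5.2) | Yes, for SAEs neither fatal nor life-threatening |
| Feasibility events (7.4, 10.2.1) | Possibly: the rule concerns changes that may be attributable to the drug |

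On late SAEs: the last planned dose is on day 36 and surgery on day 50. Thirty days after the last dose is day 36 + 30 = 66, which is post-operative day 66 − 50 = 16. The synopsis runs formal safety assessment to post-operative day 90. If being on study does not cover follow-up, SAE recording under 7.3 from about day 16 to day 90 rests on suspected causation.

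On feasibility: the boundaries are 2 to 6 events depending on the number of patients, so setting aside one event can move the decision. Section 10.2.1 also says that no increase in surgical difficulty is anticipated, which makes it harder to call such an effect expected.

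**Step 5. How thin the prior experience is.** Section 2.2.3.2 reports 160 treated adults. The chance that an event of true incidence p was never observed among them is (1 − p)^160. The incidences are assumptions:
- p = 0.5%: 0.995^160 = 45%
- p = 1%: 0.99^160 = 20%
- p = 2%: 0.98^160 = 4%

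This is the chance of not having been observed. It is not the chance of being unexpected, because an unobserved event may still be predicted from the mechanism.

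**The case against.** The strongest reply has four parts.

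First, an event with clear timing meets one listed criterion, and Unrelated also says clearly not related, so the event is not forced into Unrelated. This is a fair reading, and a reader who infers that every new toxicity is scored Unrelated by rule goes further than the text. But on this reading the event has no category, which is still a defect in a binding table.

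Second, expected is wider than seen before. The protocol itself mentions cytokine release, immune-inflammatory or autoimmune events, adrenal binding and prostatic immune infiltrate. Much immune toxicity could be called expected on mechanism. This stands, and it narrows the defect to events that are neither known nor expected.

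Third, the main safeguards do not use Table 3. A reader might infer that the primary safety result or expedited reporting is compromised. The documents do not support that. Events are recorded and counted whatever their cause, SAEs reach the IND sponsor within 24 hours regardless of causality, 7.5.1 carries its own test without citing Table 3, and dosing is held for any event of grade 3 or higher while relatedness is assessed. This stands too.

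Fourth, a reader might infer that post-operative events can never exceed Possible, because Probable needs confirmation on stopping or reducing, the plan says "No dose reductions are allowed", and surgery follows the last planned dose by 14 days. Stopping is allowed, however, and improvement during washout may be visible. Section 2.3.2 says the distribution and terminal half-lives "were estimated at 1.6 days and 25 days, respectively", and post-operative day 90 is 14 + 90 = 104 days after the last dose, or 104/25 = 4.2 terminal half-lives. More to the point, no stated action depends on Probable rather than Possible.

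**Conclusion.** The point holds with moderate severity. Table 3 gives no related category to a plausibly timed event that is neither known nor expected (0 of 4 rows), and this contradicts the reasonable-possibility standard in 7.5.1. The finding rests on the wording alone and on investigators applying the table as written. Many would use judgement, but the text does not provide for it.

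The effect is confined to the causality summary, relatedness-dependent discontinuation, late SAE recording, IRB/IBC timing for SAEs that are neither fatal nor life-threatening, and perioperative attribution as far as it feeds the feasibility rule. The number of events affected cannot be derived from the documents. No sample size, endpoint definition or all-cause safety estimate changes.

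**What to change.** - In Table 3, make a known or expected pattern a supporting feature instead of a required one, at least for Unlikely, Possible and Probable.
- State that an event with plausible timing and a reasonable possibility of drug causation is at least Possible, whether or not it has been seen before. Table 3 then agrees with 7.5.1.
- Make clear whether the criteria named in the Unrelated row are whole rows or single conditions.
- Use one set of labels: the Appendix C form has Probably Unrelated where Table 3 has Unlikely.
- Check Sections 6.4.5, 7.3, 7.4, 7.5.2 and 10.2.1 against the revised table so that related and attributable mean the same throughout. This is a reconciliation of wording and needs no new clinical rule.
- Optionally, ask for confirmation on stopping only where it can be observed.

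The cost is the wording of one table and one form. Slightly more events will be classed as possibly related, so the drug-related rates will look a little less favourable. Patients had already been treated before the expansion, so the causality summary should say which version of the table each event was scored under, or those events should be reviewed again.

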10.4 Safety Analysis

10.4.1 Evaluation of adverse events

Treatment-emergent adverse events will be translated from investigator terms to MedDRA version 6.0 terminology and summarized (number and percentage of patients) for all patients who receive at least one dose of the study drug(s). Adverse event summaries will be organized by body system, frequency of occurrence, intensity (*i.e.*, severity grade), and causality or attribution. Patients who experience an adverse event more than once will be counted only once. The occurrence with the maximum severity will be used to calculate intensity.

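### Table 3 (section 7.1.3) has no causality level for a well-timed, expected event with no other explanation when the drug was not stopped or reduced, so by default it is Unrelated

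*Combined protocol and SAP*

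**What the plan says.** Section 7.1.3 makes Table 3 the deciding rule for causality. Apart from timing and a known pattern, which all four levels above Unrelated share, the levels differ as follows:

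- **Unrelated:** the lead sentence describes an event with clearly no link to the drug; the parenthesis defines it as "An event that does not meet any of the criteria below".
- **Unlikely:** "AE is doubtfully related to the study drug", with the patient's clinical state a more reasonable explanation.
- **Possible:** the same timing and pattern, "but that could just as readily be attributed to a number of other factors".
- **Probable:** an event "that is confirmed by stopping/reducing the drug dose; and that could not be reasonably explained by the characteristics of the patient's clinical state".
- **Definite:** improvement on stopping or reducing, and recurrence on repeated exposure.

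On dosing, section 6.4.5.1 says: "Study drug administration may continue despite observation of drug-related low grade adverse events (CTCAE grade 1 or 2". It lets the investigator delay a dose for a clinically significant or unduly long low-grade event, and adds: "No dose reductions are allowed". It also ends treatment for grade 2 events of 14 days or more that are rated at least possibly related.

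On analysis, section 10.4.1 says: "Adverse event summaries will be organized by body system, frequency of occurrence", followed by intensity and causality.

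**The concern.** Probable combines two separate things: the absence of another explanation, and a positive result from stopping or reducing the drug. No level has the first without the second. An expected reaction with the right timing and no rival cause, in a man who simply carries on with treatment, is left to the default row. That row is the lowest on the scale, so the event ranks below one for which a rival cause is just as likely.

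Safety and tolerability are primary objectives (section 1.1), and causality is one of the axes on which the events are tabulated. If the table is applied as written, some events are under-attributed. If investigators set the wording aside and use judgment, the rating depends on who makes it. The attribution also matters for conduct, because the rule for prolonged grade 2 events in 6.4.5.1 depends on relatedness.

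**Working it through.** No sample size or power figure is involved, so the check is to apply the definitions to every combination of facts.

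**Inputs (Table 3).** Hold timing reasonable and pattern known. Let the other explanation be none, equally likely or more likely. Let the stopping evidence be: no confirmation; confirmed by stopping or reducing; or confirmed and recurring on re-exposure. That gives 3 × 3 = 9 combinations.

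| Other explanation | No confirmation by stopping or reducing | Confirmed | Confirmed and recurred |
|---|---|---|---|
| None reasonable | **Unrelated (by default)** | Probable | Probable and Definite |
| Equally likely | Possible | Possible | Possible and Definite |
| More likely | Unlikely | Unlikely | Unlikely and Definite |

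**Reading the grid.** As the rival explanation strengthens, the middle column runs Probable, Possible, Unlikely, which is the intended order. The left column runs Unrelated, Possible, Unlikely. One cell of nine falls to the default row, and it is the one in which nothing else explains the event. The left column also mixes a stopping test that was never done with one that was done and failed; Table 3 does not separate them.

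**Against the surrounding text.** The result contradicts the lead sentence of the Unrelated row, because an investigator who sees no other cause cannot say that a link is clearly absent. It also contradicts 6.4.5.1, which speaks of low-grade events as drug-related while dosing goes on.

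**Where the stopping test is available.**

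- *Non-infusion grade 1-2 events:* dosing may continue and reductions are ruled out (6.4.5.1). Stopping is possible through a delay, but not routine.
- *Grade 2 infusion reactions:* the infusion is stopped (6.4.4.2), so the test can be met.
- *Grade 3 or higher during dosing:* the drug is held (6.4.5.2), so the test can be met. Some grade 3 infusion reactions may be re-challenged (6.4.4.3).
- *Events that begin after the last dose on day 36:* no later dose remains to be stopped, while formal safety assessment runs to the 90th postoperative day (Synopsis, Safety analysis).

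The empty cell is therefore reached mainly through the first and last of these.

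**Where the rating is used.** It enters the summaries in 10.4.1 directly. It also supplies the attribution behind the at-least-possibly-related wording in 6.4.5.1, since Table 3 is the only causality scale with stated criteria. A prolonged grade 2 event that defaults to Unrelated would not literally meet that wording.

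**The case against.** The strongest reply is that a sensible investigator would not call such an event Unrelated. The lead sentence of that row points away from it, 6.4.5.1 treats such events as drug-related, and Possible is the natural choice. On this view the fault is an ambiguity between a lead sentence and a parenthesis. That is fair as a prediction of behaviour. But choosing Possible means disregarding its written criterion, and the table is stated to be decisive.

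Four stronger readings might be inferred, and the documents do not support them:

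- **That events of grade 3 or higher can never be confirmed by re-exposure.** Section 6.4.5.2 allows for exceptions stated elsewhere, and 6.4.4.3 provides one.
- **That the related-event rates in 2.2.3.2 give the number of men misclassified.** They do not say how many events lacked another explanation. Chills, nausea and vomiting are also listed there as infusion-reaction symptoms, which fall under 6.4.4. Many low-grade events will have a competing cause and be rated Possible.
- **That the long half-life makes stopping uninformative.** The half-lives "were estimated at 1.6 days and 25 days, respectively" (distribution and terminal). Using the terminal value, postoperative day 30 is 30/25 = 1.2 half-lives after surgery and day 90 is 90/25 = 3.6. Concentration falls to about 2^-1.2 = 44% and 2^-3.6 = 8% of its level at surgery. An event present at the last dose can be watched as exposure falls.
- **That the main safety result is biased.** The adverse event rate (8.2.1, 10.2.1) has no causality filter, 7.5.2 requires serious events to be notified regardless of causality, and the infusion-reaction part of the toxicity stopping rule counts events by grade and duration.

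**Conclusion.** The gap is real and follows from the wording of Table 3 alone. It affects one of nine combinations, and in that one the ordering is inverted. In practice it concerns mainly non-infusion grade 1-2 events without a dose interruption and events that begin after the last dose.

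The consequence is possible under-attribution in the causality summaries of 10.4.1, and an unreliable basis for the relatedness wording in 6.4.5.1. The number of events cannot be estimated from the documents, because it depends on how many have no other explanation and on how investigators resolve the conflict within the Unrelated row.

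The conclusion assumes that Table 3 is applied as written, that the event's timing is reasonable and its pattern known, and that its cause was not confirmed by stopping or reducing the drug. It is worth correcting because the scale feeds a reported safety table and the correction is small.

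**What to change.** In Table 3:

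- Define Probable as plausible timing and an expected pattern, not reasonably explained by the patient's clinical state, surgery or other drugs. Treat improvement after stopping as supporting evidence where it was observed, not as a requirement.
- Keep improvement on stopping and recurrence on re-exposure as requirements for Definite.
- Limit Unrelated to events with another clear cause or no plausible timing, and remove the catch-all parenthesis.

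State in 10.4.1 that causality is summarised on this scale. The left column of the grid then runs Probable, Possible, Unlikely, in line with the middle column. The attribution wording in 6.4.5.1 should be reconciled with the revised table; no dosing rule needs to change.

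The cost is the rewording of one table and the matching case report form choices. Visits, sample size and stopping boundaries stay as they are. The downside is that somewhat more events will be shown as probably related.
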